### **Study Procedures:**

Five hundred individuals will be screened with the goal of consenting 50 patients and 20 patients completing the study. The study consists of 8 study visits including 4 testing days, one before (V2) and one on the day of the fifth session of tDCS (V6) followed by the structured 16-week long behavior modification class, and test visit half way through the 16-week class (V7) (2 months into the behavior modification class), and a final test visit 2 months later (+/- 2 weeks) (V8). At consent/screening visit (V1), baseline serum biochemistries, a general physical (including weight measurement) pregnancy test, impulsivity questionnaire (Binge Eating Scale [BES], depression screening (PHQ-9 [<https://patient.info/doctor/patient-health-questionnaire-phq-9>]), Minnesota Blast Exposure Screening Tool (MN-BEST), and executive function-related testing (NIH Examiner and Brain HQ) will be performed; these can be completed at V2 if those were not completed after consent on V1. These tests; other than the pregnancy, biochemistries, and PHQ-9; are repeated at V6-V8. While subjects are undergoing the 5 days of tDCS treatments (V2-V6) they will undergo Brain HQ testing during the treatment sessions. PHQ-9 is repeated at the final visit.

### **Study Visit Details:**

#### ***Screening visit (Visit 1 [V1]):***

Subjects will be recruited from the clinic where Drs. [name] and [name] attend. Interested subjects will be screened for inclusion/exclusion criteria and review study details. Medical records will be reviewed for eligibility, and interested subjects will be consented if they are eligible. They will then undergo baseline blood draw (to include a comprehensive metabolic panel if not available within last 6 months, directed history and physical (including a weight measurement). If thyroid tests, (TSH alone or a TSH with a free T4), were not done and normal in the last 3 months for individuals taking thyroid hormone replacement, these will be done at baseline assessment. Baseline testing including the NIH Examiner Battery (which measures executive function domains), MN-BEST and BES (may either be done at the end of V1 or beginning of V2).

#### ***tDCS session visits (V2-6):***

Subjects will go to the Minneapolis VAMC GRECC where they will undergo the tDCS sessions. Subjects will be randomly assigned to active vs. sham treatments which will occur on 5 sequential weekdays. The tDCS session will include a pre/post symptom rating questionnaire, 13 minutes of stimulation, a 20-minute stimulation break, followed by 13 more minutes of stimulation. Subjects will complete the Brain HQ test during stimulation and the stimulation break. The final stimulation visit, V6 will include NIH Examiner and their weight will be collected. These sessions will last around 1 hour to 1.5 hours each.

#### ***Visits post tDCS intervention (V7 and V8):***

These visits will be identical to V1 with the exceptions that the history and physical, MN-BEST and blood draw will not be repeated; a weight measurement will be taken along with completion of the BES questionnaire, the Brain HQ and NIH Examiner. A short blinding questionnaire will be asked at V8 to assess the adequacy of tDCS blinding.

Table 1. Table of Assessments

Visit	Assessments	Stimulation	Duration	Compensation
Visit 1	HIPAA, Consent, NIH Examiner, BES, PHQ-9, Medication Review, MN-BEST, Blood Draw, Physical (Weight Measurement), Pregnancy Test (if applicable)	None	120 minutes	\$30
Visit 2-5	tDCS, Pre/Post SRQ, Brain HQ, Medication Review	tDCS	60 minutes	\$15
Visit 6	tDCS, Pre/Post SRQ, Brain HQ, NIH Examiner, Medication Review, Weight Measurement	tDCS	90 minutes	\$22.50
Visit 7-8 (follow-ups)	NIH Examiner, Medication Review, Brain HQ, BES, Weight Measurement, Visit 8 only: PHQ-9, Blinding Questionnaire	None	120 minutes	\$30
Total:			11.5 hours	\$ 172.50

tDCS Device: We will use the Neuroelectrics Starstim system, a wireless multichannel transcranial current stimulator. Periods of tDCS stimulation of 13 minutes will be twice a day, separated by 20 minutes, for five consecutive days (5 total tDCS stimulation sessions). Active tDCS: A 2-mA current will be administered via two circular carbon rubber core electrodes in saline-soaked surface sponges (25 cm^2), placed in a neoprene headcap with marked locations based on the 10-10 EEG system. The anodal stimulating electrode will be at location F4, over right dorsolateral prefrontal cortex (DLPFC) and cathodal electrode at location F3, over left DLPFC. This tDCS configuration has been shown to be effective for stimulating DLPFC. Sham tDCS: For sham stimulation, the electrodes will be placed at the same positions as for active stimulation (F3 and F4), but current will be ramped down immediately after the initial 30 s ramp up period. Thus, participants will feel the initial itching sensation associated with tDCS but will receive no active current for the rest of the stimulation period. This method of sham stimulation has been shown to be reliable (Gandiga, Hummel, & Cohen, 2006). The Starstim software supports the measurement of electrode impedance. Before each training session, the impedance of the electrodes will be checked and verified to be ≤10 KOhm. During a training

session, the impedance is measured every second and if found to be  $> 20$  KOhm stimulation will be terminated for safety. The current and impedance will be recorded for every session.

Computerized cognitive training during the tDCS or sham sessions: We will utilize Brain HQ Cognitive Training software ([www.brainhq.com](http://www.brainhq.com)).

Untrained tests (to evaluate for generalization at the beginning and end of the study):

As done by Galioto and predictive of weight loss success in individuals with obesity (Galioto 2016), we will utilize four components of the NIH EXAMINER battery, a validated computerized battery of experimental tests to assess four domains of executive function before and after the weight loss period.

Domains:

*a. Working memory*

The Dot Counting Test. Subjects will count and remember the number of blue circles in a display of other shapes. There are six trials in which the number of displays presented in each trial increases from two to seven. Participants are instructed to recall, in order, the total number of blue circles on each display and the correct responses are recorded.

*b. Inhibition*

The Flanker test. Subjects must make rapid decisions about the direction of central stimuli when surrounding items are congruent, pointed in the same direction or incongruent, pointed in the opposite direction. Lower scores on this domain are related to poor impulse control.

*c. Set shifting*

The Set Shifting task. A stimulus at the time of the screen must be matched to either of two stimuli in the corner of the screen on one of two types of characteristics (color and shape). The matching characteristic alternates in a pseudorandom fashion. Cognitive flexibility is evaluated with this task. Lower scores on this domain are related to greater behavioral compulsivity.

*d. Planning*

The Unstructured Task. A number of simple puzzles are completed, with differing point assignments (high and low value puzzles). Subjects must plan the order in which they do the puzzles to obtain as many points as possible in 6 minutes. Puzzles with various assigned point values in order to obtain as many points as they can in 6 minutes.

Other instruments:

*a. PHQ-9*

Mood will also be assessed at the beginning and end of the study.

The Patient Health Questionnaire. The PHQ-9 will be used to assess nine DMS-IV-TR criteria for depression. Scores range from 0 to 27 with higher scores being consistent with more depressive symptoms.

*b. Binge Eating Scale (to be done at the same timepoints as the untrained cognitive testing)-*

The BES is a 16-item questionnaire assessing the presence of binge eating behaviors. The questions are presented as groups of statements about behavior, thoughts, and emotional states. Individuals indicate which statement in each group best describes how they feel. Higher scores are consistent with more binging behavior.

*c. Minnesota Blast Exposure Screening Tool (MN-BEST)*

The MN-BEST is a semi-structured interview to collect self-reported information. Using the instrument, the three most significant blast exposure events will be recorded in addition to the frequency and duration of post concussive symptomatology. A similar appraisal will be made of

the three most significant impact head injuries for the person in their lifetime. This information will then be used to make determinations about the presence of TBI from the events.

*d. Blinding Questionnaire*

The blinding questionnaire is a short, 3 question assessment administered by research staff at the end of study participation. The purpose of the questionnaire to assess the adequacy of tDCS blinding.

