## 6. Study Methods, Procedures, and Statistical Plan

### Study Design:

For this single-site pilot study our statistical approach will be similar to prior work done by members of our team previously, a double-blind, randomized controlled design with participants randomized to either active or sham tDCS. For this study Veterans will be referred as potential candidates because they have obesity and self-report that they tend to have at least one occasion of out-of-control eating per week on average. Participants will be trained on the Brain HQ, an interactive computer software package in which subjects work through a series of structured exercises designed to stimulate neuroplasticity. Participants will be randomly assigned to receive either active tDCS or sham stimulation with their training during one hour session each day( 13 minutes of stimulation , 20 minute stimulation break, followed by 13 more minutes of stimulation) over five days. A 2 mA current will be applied with two 25 cm^2 saline soaked electrode sponges with anode at F4 (right) and cathode at F3 (left) concurrent with the Brain HQ. To evaluate generalization, an untrained NIH Examiner Battery sub-set testing 4 modalities of executive function will be performed before and after the five days of training. Subjects will then go through the Move Mass Behavior Modification after completing the five days of treatment. (This 16-week structured behavior modification program of bi-weekly sessions is usual care for these participants.) Participants will return for the trained and untrained testing at V7 (halfway through the behavior modification course) and V8 (final study visit to occur after the behavior modification course) follow-up sessions without stimulation. For the trained Brain HQ tasks, growth curve analysis (GCA) examining individual variation of the

growth rates over time will be done (across the 5 days of tDCS sessions and the subsequent follow-ups) to examine for change in individual and group trajectories over time. For the untrained NIH Examiner tasks, GCA will be used to evaluate for individual and group effects in executive function in the four domains of the NIH Examiner Battery from pre- to post-treatment and through follow-up sessions. We will also compare pre- and post- treatment results in the cravings and binging questionnaires within and between groups.

Figure 1: Study Visit Schedule

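### Study Procedures schedules the Binge Eating Scale at V6, but the Visit 6 row of Table 1 omits it, leaving no score between the end of treatment and the class if the table is followed

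*Combined protocol and SAP*

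**What the plan says.** Two sections put the BES at V6.

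- Study Procedures names the BES among the tests done at V1 (or V2), then states: "These tests; other than the pregnancy, biochemistries, and PHQ-9; are repeated at V6-V8". The BES is not among the exceptions.
- The BES entry under Other instruments says the scale is "to be done at the same timepoints as the untrained cognitive testing". The untrained testing is the NIH Examiner subset. Study Design has it "testing 4 modalities of executive function will be performed before and after the five days of training", and the V2-6 visit text is explicit: "The final stimulation visit, V6 will include NIH Examiner and their weight will be collected".

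Table 1 does not put it there. Its Visit 6 row reads "tDCS, Pre/Post SRQ, Brain HQ, NIH Examiner, Medication Review, Weight Measurement". The Visit 1 row and the Visit 7-8 row both list the BES, and the text for V7 and V8 also names it.

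Two further statements bear on the consequence. Study Design promises a comparison of binge and craving questionnaires before and after treatment, in each arm and across arms. Study Procedures describes V7 as a "test visit half way through the 16-week class (V7) (2 months into the behavior modification class", with the class starting after the five treatment days.

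**The concern.** Site staff usually work from the assessment table. If they do so here, nobody completes a BES at V6, and a score missed on that day cannot be recovered.

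The BES is the only eating questionnaire in Table 1, so the binge comparison in Study Design rests on it. That section treats post-treatment and follow-up as different occasions and calls V7 and V8 follow-ups, as does the table's own row label. V6 is therefore the natural post-treatment visit. Without it, the earliest scheduled value after baseline comes when participants have already had about half of a behavioral weight-loss program. A change seen within an arm could then come from stimulation with training, from the class, or from both. A difference between arms could not be dated to before or after the class began.

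**Working it through.** No sample-size or power figure is involved. The check sets the schedules side by side.

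| Visit | NIH Examiner (Table 1) | BES (Study Procedures) | BES (Table 1) |
|---|---|---|---|
| V1 (or start of V2) | yes | yes | yes |
| V2-V5 treatment sessions | no | no | no |
| V6 | yes | yes | **no** |
| V7 | yes | yes | yes |
| V8 | yes | yes | yes |
| Total | 4 | 4 | 3 |

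**Was the table read intact?** Its totals were re-added:

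- Time: 120 + 4 × 60 + 90 + 2 × 120 = 690 minutes = 11.5 hours, as stated.
- Payment: 30 + 4 × 15 + 22.50 + 2 × 30 = $172.50, as stated.

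The rows appear complete, although totals cannot prove that no entry was lost from a cell.

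**How many scores are at stake?** Under Table 1 there are no V6 BES scores. Under Study Procedures there is one for each participant who reaches V6: 20 if only the planned completers do, and up to 50 if everyone enrolled does.

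**What does each contrast measure without V6?** Write A for the change due to active stimulation with training, S for the change under sham with training, and C for the change due to the class up to V7.

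- Within the active arm, baseline to V7: A + C. Within the sham arm: S + C. Neither isolates the treatment week.
- Between arms at V7: (A + C) − (S + C) = A − S. If the class works differently after active stimulation, the contrast includes that difference too. It is still a randomized comparison of the two assignments at that visit.

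So the within-arm reading is blurred, and the between-arm reading is sound but late.

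**Does a V6 entry alone give a post-treatment score?** Not quite. Study Procedures places this testing on the day of the fifth session and does not say whether it precedes or follows stimulation. The order has to be stated.

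**The case against.** Several points on the other side are fair.

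- The repeat sentence in Study Procedures is loose. Read literally, it would also repeat the MN-BEST and the physical, which the V7 and V8 text excludes. It may therefore not have been meant as an exact list. This stands, but the BES entry under Other instruments points to V6 separately.
- That second link is an inference. The heading for the untrained tests describes them more loosely, as "to evaluate for generalization at the beginning and end of the study". This also stands, but the conflict between Study Procedures and Table 1 does not depend on the link.
- The V6 sentence in the visit text is weak evidence of omission. It does not claim to be complete, and it also leaves out the medication review that Table 1 requires at V6. A reader might infer from the sentence and the table together that the sponsor decided to drop the BES at V6. The documents do not show this. The Visit 1 row also lacks Brain HQ, which Study Procedures lists at baseline, so loose drafting is at least as likely.
- A fifth-day BES may show little. Referral is based on about one out-of-control episode per week, and the baseline BES may be as late as the start of V2. This limits what a V6 score can add. It is a reason to keep V7 and V8, not a reason to leave the schedules in conflict.
- The background cites early questionnaire effects, and a reader might take this as showing that an early BES is essential. Those passages concern cravings questionnaires and unspecified questionnaires, not the BES, so they are not relied on here.

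**Conclusion.** The inconsistency is real, and it affects which data are collected. Following Table 1 gives three scheduled BES occasions instead of four. None falls between the end of treatment and the class, and the first after baseline is about 2 months into a 16-week program.

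A reader might infer more: that the binge comparison cannot be run, that the class biases the comparison of arms, or that the trial's main results are at risk. The documents support none of these. The comparison can be run at V7 and V8. Both arms are offered the same class after randomization. The named endpoints are the NIH Examiner score and weight, both of which Table 1 schedules at V6. The BES is not a named endpoint, and the Statistical Plan and Power Analysis section does not mention it.

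This is a minor-to-moderate issue for a supporting outcome. The conclusion assumes that staff follow the table and that V7 falls near its described midpoint; no separate window for V7 is clearly stated. It concerns scheduled visits only: an early end-of-study visit could give a withdrawn participant an earlier BES.

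**What to change.** Reconcile Study Procedures, the V2-6 visit text, Table 1 and the BES entry under Other instruments:

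- Add the BES to the Visit 6 row of Table 1 and to the V6 sentence, to be completed after the second stimulation period of the fifth session.
- State in Study Design that V6 is the post-treatment BES and that V7 and V8 are follow-up. Keep V7 and V8 in the BES analysis.
- While editing Study Procedures, name the tests repeated at each of V6, V7 and V8.

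If leaving the BES out at V6 is intended, correct Study Procedures and the BES entry instead, and name the visit that Study Design means by post-treatment.

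The cost is one 16-item questionnaire at an existing visit, plus a few text edits. The documents do not give its completion time. V6 is already listed at 90 minutes, the top of the range in the visit text, so the V6 time and payment entries and the table totals may need a small update.

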### **Statistical Plan and Power Analysis**

For this pilot study our statistical approach will be similar to prior work done by members of our team, a randomized controlled design with participants randomized to either active or sham tDCS.

Power Analysis. For Aim 1, the primary comparison will be difference in change before and after training on untrained impulsivity-related tests of executive functioning between active and sham tDCS. [name] and colleagues' preliminary data found an effect size of  $d=.97$  between active and sham tDCS groups. Based on these results, the current pilot project is powered to detect an effect size of .97 with 80% power and an alpha = .05 (N = 20). Power to detect a medium effect size will be approximately .60. Thus, this study is well-powered to detect changes on the primary cognitive outcome variables.

For the secondary aim of weight loss, an ANOVA will be used with weight as the dependent variable and the grouping variable will be active vs. sham. We will be testing for a Group x Time interaction for weight.

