#### **4. Study Endpoints**

**Primary Endpoint:** decrease in impulsivity and compulsion (as measured by change in NIH Examiner Score) with active tDCS compared to sham

**Secondary Endpoint:** change in weight over the study period

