## **14. Data Management**

Data Analysis Plan: For this pilot study participants will be randomized to either active or sham tDCS. For the trained task, growth curve analysis (GCA) examining individual variation of the growth rates over time will be done (across all 10 tDCS sessions and the subsequent follow-ups) to examine for change in individual trajectories over time. For the untrained task (NIH Examiner), GCA to evaluate for enhancement of executive function in the four domains from pre- to post-treatment as compared with the sham group will be analyzed. As a secondary aim we will evaluate weight loss response during and after the behavior modification program

and evaluate the effect of active vs. sham treatment on weight loss. Results from this study will inform larger follow up studies supported by external applications.

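### The primary contrast is a difference in change on the NIH Examiner, and no section specifies adjustment for the baseline score the trial already collects

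*Combined protocol and SAP*

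**What the plan says.** The Aim 1 contrast is given in section 6, Statistical Plan and Power Analysis: "the primary comparison will be difference in change before and after training on untrained impulsivity-related tests of executive functioning between active and sham tDCS". Section 4, Study Endpoints, matches it. Impulsivity and compulsion are to be judged "as measured by change in NIH Examiner Score".

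The model appears in two other places, described differently:

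- Section 6, Study Design: "GCA will be used to evaluate for individual and group effects in executive function in the four domains of the NIH Examiner Battery". That sentence carries the analysis through the follow-up sessions as well as pre- to post-treatment.
- Section 14, Data Analysis Plan: "GCA to evaluate for enhancement of executive function in the four domains from pre- to post-treatment as compared with the sham group". Follow-up is not mentioned there for the Examiner.

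The baseline score will be in hand. The screening-visit text lists "Baseline testing including the NIH Examiner Battery (which measures executive function domains), MN-BEST and BES", to be done at the end of V1 or the start of V2. Study Procedures counts four testing days: one before treatment, then V6, V7 and V8. For the questionnaires, Study Design plans to "compare pre- and post- treatment results in the cravings and binging questionnaires within and between groups".

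No section mentions a baseline covariate, ANCOVA or a common baseline mean, and none states the growth model's group intercept or time coding.

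**The concern.** A change score fixes the coefficient on baseline at 1. When the correlation between the pre and post scores is below 1 and their variances are equal, the best coefficient is r. The excess, 1 − r, stays in the estimate multiplied by whatever gap the arms happen to have at baseline. An arm that starts lower will tend to show more improvement through regression to the mean.

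With 20 participants, sizeable gaps are common. A reader who saw one in the baseline table could not tell how much of the estimated effect came from it. The unadjusted contrast also gives up some precision unless r is high. Section 14 says the results will inform larger studies, so the estimate itself matters as well as the test.

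**Working it through.** **Inputs from the documents.** 10 per arm (Study Summary); d = 0.97, alpha 0.05, N = 20 (Statistical Plan and Power Analysis).

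**Assumptions.** Two-sided test, since sidedness is not stated. Equal variance before and after. d = 0.97 is taken on the change scale, because the plan does not say which scale it refers to. r ranges from 0.5 to 0.9, since none is given. Scores are in baseline SD units.

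**Step 1: the plan's own figure.** The project is said to be "powered to detect an effect size of .97 with 80% power and an alpha = .05 (N = 20"). For a two-sample t test of change:

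- Noncentrality = 0.97 × √(10/2) = 2.17 on 18 df, which gives power of 53.7% two-sided (67.1% one-sided). The stated 80% does not reproduce.
- The plan adds: "Power to detect a medium effect size will be approximately .60". Taking medium as d = 0.5, power is 18.5% two-sided (28.5% one-sided).

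This discrepancy is a separate issue. The 53.7% is used below only as the base for comparison.

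**Step 2: what the growth model gives.** If each arm has its own intercept and all pre and post scores are present, the pre/post group-by-time term equals the difference in mean change. If both arms share a baseline mean, the V6 contrast is close to ANCOVA. The text permits either.

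**Step 3: precision.**

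- Var(change) = 2(1 − r) × 2/n
- Var(ANCOVA) = (1 − r²) × 2/n × (N − 3)/(N − 4)
- Ratio ANCOVA/change = (1 + r)/2 × 17/16 at N = 20

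| r | Variance ratio | Change power | ANCOVA power (17 df) |
|---|---|---|---|
| 0.5 | 0.75 × 1.0625 = 0.80 | 54% | 63% |
| 0.6 | 0.80 × 1.0625 = 0.85 | 54% | 60% |
| 0.7 | 0.85 × 1.0625 = 0.90 | 54% | 58% |
| 0.8 | 0.90 × 1.0625 = 0.96 | 54% | 55% |
| 0.9 | 0.95 × 1.0625 = 1.01 | 54% | 53% |

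Break-even: (1 + r)/2 × 17/16 = 1 gives r = 32/17 − 1 = 0.88. A simulation of 100,000 trials at each of r = 0.5, 0.7 and 0.8 gave variance ratios of 0.80, 0.90 and 0.95, and ANCOVA power of 63%, 58% and 55%.

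**Step 4: chance imbalance.**

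- SD of the baseline gap = √(2/10) = 0.447.
- A gap above 0.433 in either direction occurs in one trial in three; a gap above 0.5 occurs in about 26%.
- Conditional shift of the change-score estimate = (1 − r) × gap, in favour of the arm that started lower. At r = 0.6 and a gap of 0.433 it is 0.4 × 0.433 = 0.17 SD.
- Standard error of the change difference at r = 0.6 = √(0.8 × 0.2) = 0.40, so the shift is 0.17/0.40 ≈ 0.4 of a standard error.
- In the simulation, the correlation between the estimate and the baseline gap was −0.50 (r = 0.5) and −0.39 (r = 0.7) for change scores, and about 0 for ANCOVA.

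**The case against.** The strongest reply is that the plan has not committed itself to an unadjusted analysis. The change wording sits in the power paragraph, and under randomization ANCOVA estimates the same quantity. The growth model is under-specified and could be fitted with a common baseline mean. This stands in part. A reader might infer that the plan never adjusts for baseline, but the documents show only that no section specifies adjustment. They do not rule it out. What remains is that the one contrast stated explicitly is a difference in change, and the endpoint definition agrees with it.

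A reader might also infer that the Examiner growth curve has only two occasions and so cannot separate individual growth from measurement error. Section 14 alone suggests this. Study Design, however, runs the model through follow-up, and Study Procedures gives four testing days, so the inference fails.

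A third tempting reading is that the change score is biased. It is not. Averaged over randomizations it is unbiased, it keeps its type I error, and its standard error already allows for chance imbalance. The shift in Step 4 is conditional on the gap in the trial at hand, and the usual one is a fraction of a standard error.

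Finally, the gain depends on an r that the documents do not supply, and above about 0.88 there is none. That is correct. But the loss at r = 0.9 is under one power point, so the risk of adjusting is small.

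**Conclusion.** The point holds in a limited form. The stated primary contrast is a difference in change, the baseline Examiner score is available, and no section specifies its use as an adjustment. A baseline-adjusted contrast would be protected from chance imbalance. It would also gain about 9 power points at r = 0.5, 4 at 0.7 and 1 to 2 at 0.8, with nothing gained at 0.9. These figures rest on equal pre and post variances, a two-sided 5% test, d = 0.97 on the change scale and 20 complete pairs. The growth model does not settle the matter, because its baseline handling is unstated and its two descriptions differ on follow-up.

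This is an inexpensive improvement worth making before unblinding. It is not a defect that invalidates the trial. It should not be read as a cure for the power claim: ANCOVA reaches 63% at most across r = 0.5 to 0.9.

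**What to change.** In the Statistical Plan and Power Analysis, state the primary contrast as the active-sham difference in each prespecified primary Examiner score at V6, adjusted for the participant's own pre-treatment score (ANCOVA). The practically equivalent alternative is a V6 contrast from the longitudinal model, with time as categorical and both arms constrained to a common baseline mean. Name one of the two as primary.

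Then bring Study Endpoints, Study Design and the Data Analysis Plan in section 14 into line, so that endpoint, occasions and model agree. Use the same baseline-adjusted form for V7 and V8, and for the BES at the visits where it is collected. Study Procedures implies that the BES is repeated at V6, while Table 1 lists it only at V7 and V8 after baseline, so that also needs settling.

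The cost is wording and one degree of freedom, a negligible loss if r is about 0.9 or higher. No new data are needed. The stated 80% power needs its own correction.
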